6.4 Treatment Withhold, Dose or Schedule Reduction, or Discontinuation for Toxicity

If an adverse event (AE) occurs, the Investigator should determine if the AE could be attributed to either drug (AM0010 or pembrolizumab) or both, or if other factor(s) were the cause of the AE. Continued treatment with the study drugs is based on the Investigator's assessment of risk-benefit per the guidelines outlined below. Both the study drugs in Arm 1 should be discontinued if 1 study drug is discontinued.

6.4.1 Treatment Withhold and Discontinuation

6.4.1.1 AM0010

AM0010 dosing will be withheld or permanently discontinued based on the criteria provided in [Table 2](#).

Table 2. Toxicity Management Guideline for AM0010

Toxicity/Adverse Event	Toxicity Grade (CTCAE) or Conditions	Action Taken to AM0010
Fatigue	Grade 3 or 4	Withhold
AST, ALT	Grade 3 or 4 >5-10×ULN for >2 weeks; drug-related >10×ULN; drug-related	Withhold Permanently discontinue Permanently discontinue
Total bilirubin	Grade 3 or 4 >5×ULN; drug-related	Withhold Permanently discontinue
Concurrent AST or ALT and total bilirubin elevation	AST or ALT>3×ULN and total bilirubin >2×ULN; drug-related	Permanently discontinue
Alkaline phosphatase	Grade 3 or 4	Withhold
Diarrhea, nausea, vomiting, abdominal pain, or bloating	Grade 3 or 4	Withhold
Other non-hematologic toxicities with an impact on organ function	Grade 3 or 4	Withhold
Skin drug-related AE	Grade 3 or 4	Withhold
Any adverse event, laboratory abnormality, or intercurrent illness	Presents a substantial clinical risk to the patient in the judgment of the Investigator	Permanently discontinue
Any adverse event including laboratory abnormalities, except 
 Grade 4 neutropenia ≤21 days Grade 4 lymphopenia or leukopenia <21 days 	Grade 4; drug-related	Permanently discontinue
Any event	Life-threatening and related	Permanently discontinue

Toxicity/Adverse Event	Toxicity Grade (CTCAE) or Conditions	Action Taken to AM0010
Any adverse event, laboratory abnormality, or inter-current illness that, in the judgment of the Investigator, warrants delaying the dose	Grade ≥ 2	Withhold
Any dosing delay	Lasting >12 weeks	Permanently discontinue
Thrombocytopenia	Grade 3 or 4 Grade 3 or 4 with Grade 3 or 4 bleeding; drug-related	Withhold Permanently discontinue
Anemia	Grade 3 or 4	Withhold

Notes:

- AM0010 doses may be withheld for ≤ 12 weeks (ie, up to 84 consecutive doses).
- AM0010 doses should be withheld until resolution to Grade 1 or pretreatment baseline.
- Withholding dose to allow prolonged steroid tapers to manage drug-related adverse events is allowed.
- Patients receiving AM0010 may receive growth factors (including G-CSF and erythropoietin) for febrile neutropenia or Grade 3 or greater anemia at the discretion of the Investigator.
- Anemia can be due to a direct effect of AM0010 on the scavenger receptor, leading to higher turnover of red blood cells. While this can be managed by withholding dose until resolution to Grade 1 or baseline, blood transfusion is permitted as well if the Investigator deems it necessary.
- Tumor assessments should continue as per protocol even if dosing is withheld.
- See [Table 3](#) for dose schedule reduction criteria for AM0010.

For Grade 3 or 4 toxicities that are related to AM0010 and do not require dose discontinuation, dose schedule reduction will be performed according to [Table 3](#).

Table 3. Dose and Dose Schedule Reduction of AM0010

Dose Schedule	Schedule Modification Criteria	AM0010
SC QD (continuous daily dosing)	-	Starting dose schedule
5 Days on/2 days off	First Grade 3 or 4 event(s)	First dose schedule reduction
4 Days on/3 days off	Second Grade 3 or 4 event(s)	Second dose schedule reduction
2 Days on/5 days off	Third Grade 3 or 4 event(s)	Third dose schedule reduction

Dosing will be withheld until return of the AE to Grade 1 or baseline. If Grade 3 or 4 toxicity occurs after 3 dose reductions of AM0010, patients will be discontinued from study. Once the dose schedule has been reduced, it should not be increased.

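### Protocol Table 2 tells sites both to withhold and to permanently stop AM0010 for a drug-related Grade 4 skin event

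*Protocol*

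**What the plan says.** Protocol Section 6.4.1.1 makes withholding and permanent discontinuation of AM0010 depend on the criteria in Table 2. Four parts of that section and one sentence in Section 6.4 matter here.

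- **Skin row.** For "Skin drug-related AE" at Grade 3 or 4, the action is to withhold.
- **General Grade 4 row.** This row begins "Any adverse event including laboratory abnormalities, except" and then lists two exceptions: Grade 4 neutropenia of up to 21 days, and Grade 4 lymphopenia or leukopenia of under 21 days. For any other event that is Grade 4 and drug-related, the action is permanent discontinuation. A separate row does the same for any event that is "Life-threatening and related", with no exceptions.
- **Anemia row and note.** The row says withhold at Grade 3 or 4 and does not mention relatedness. The note under the table says: "Anemia can be due to a direct effect of AM0010 on the scavenger receptor". It continues: "While this can be managed by withholding dose until resolution to Grade 1 or baseline", and adds that transfusion is also allowed.
- **Lead-in to Table 3.** Schedule reduction is "For Grade 3 or 4 toxicities that are related to AM0010 and do not require dose discontinuation".
- **Section 6.4.** "Both the study drugs in Arm 1 should be discontinued if 1 study drug is discontinued".

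**The concern.** A site with a drug-related Grade 4 skin event finds two rows of one table that both apply and give different actions. Under the skin row it holds AM0010 until recovery to Grade 1 or baseline and then restarts on a reduced schedule. Under the general row it stops AM0010 for good, and Section 6.4 then ends pembrolizumab too.

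Either error has a cost. A patient may be re-exposed to AM0010 after an event that another row says should end treatment, or may lose both drugs when the skin row allowed a pause. Arm 2 patients who cross over receive AM0010 as well, so they are exposed to the same ambiguity. Section 6.4.3 says that no data monitoring committee will be formed, so no such body would notice sites diverging.

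**Working it through.** No figure in the plan needs reproducing. The check compares the rows of Table 2 by event, grade, relatedness and action, and looks for a precedence rule.

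**Step 1. The two cases side by side**

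| Event | Specific row | General Grade 4 row | Result |
|---|---|---|---|
| Grade 3 skin, drug-related | Withhold | Does not apply | Consistent |
| Grade 4 skin, drug-related | Withhold | Permanently discontinue | Contradiction |
| Grade 4 anemia, unrelated | Withhold | Does not apply | Consistent |
| Grade 4 anemia, drug-related | Withhold | Permanently discontinue | Overlap; precedence not stated |

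The skin row covers only drug-related events, so its Grade 4 part lies wholly inside the general row. There is no Grade 4 case in which withholding is the only instruction. The anemia row has no relatedness limit, so its Grade 4 part still has a use for unrelated events.

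**Step 2. All withhold rows that can reach Grade 4**

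Nine rows are set at Grade 3 or 4, and one investigator-judgment row is set at Grade 2 or above: 9 + 1 = 10.

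- Direct contradiction: skin (1).
- Overlap only if the Grade 4 event is drug-related: fatigue, alkaline phosphatase, gastrointestinal, other non-hematologic, thrombocytopenia without Grade 3 or 4 bleeding, anemia (6).
- Own drug-related discontinuation tier: AST/ALT, total bilirubin (2).
- Investigator judgment: (1).

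1 + 6 + 2 + 1 = 10.

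**Step 3. Is there a precedence rule?**

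None is written in Table 2, its notes or the Table 3 lead-in. The lead-in excludes toxicities that require discontinuation, but whether the skin event requires discontinuation is the question at issue.

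**Step 4. What the two readings mean for dosing**

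After a first event on the withhold reading, Table 3 gives 5 days on and 2 off: 5/7 = 71.4% of planned AM0010.

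- At 0.8 mg/day: 7 × 0.8 = 5.6 mg/week planned; 5 × 0.8 = 4.0 mg/week after reduction.
- At 1.6 mg/day: 7 × 1.6 = 11.2 mg/week planned; 5 × 1.6 = 8.0 mg/week after reduction.

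The AM0010 rule does not stop pembrolizumab on this reading. On the discontinue reading both drugs go to 0%. These figures describe the two outcomes; they do not measure how often the conflict will arise.

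**The case against.** The best defense is that the table's structure supplies the order. Withholding is the base action and discontinuation criteria sit on top of it. In the AST/ALT, bilirubin and thrombocytopenia rows a withhold tier and a stricter drug-related tier appear together, and the stricter one governs once met. The general row then works as a catch-all with a closed list of exceptions, and the row for life-threatening related events points the same way. This stands for the six overlapping rows, where both instructions keep a purpose. It does not rescue the skin row, whose mention of Grade 4 would have no effect at all.

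A reader might infer that anemia is contradicted as squarely as skin. The documents do not support that. The anemia row has the same form as fatigue or alkaline phosphatase. Its note is permissive, names no grade and can be read as Grade 3 only. The separate growth-factor note, which covers "Grade 3 or greater anemia at the discretion of the Investigator", concerns supportive care and says nothing about AM0010 dosing. What remains is an ambiguity: the note is about anemia caused by AM0010, sets no ceiling and belongs to a table whose anemia row names Grade 4.

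The consequence is also limited. Table 2 is titled a guideline, Section 6.4 relies on the investigator's risk-benefit assessment, and a separate row allows stopping for substantial clinical risk. The catch-all row of Table 4 already discontinues pembrolizumab for Grade 4 immune-related events, so the conflict matters mainly for events attributed to AM0010 alone. But the investigator's judgment is to be exercised within the guidelines, and for skin the guideline gives two answers.

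**Conclusion.** The contradiction is real for one row: drug-related Grade 4 skin events. Six further rows lack a stated precedence that can be inferred, least securely for anemia. This rests on the wording of Table 2 and its notes alone.

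Severity is minor. The documents give no Grade 4 skin or anemia rate for AM0010, so no count of affected patients is offered. A reader might infer that uneven stopping in Arm 1 undermines the response-rate comparison. Nothing in the documents supports that: the analysis includes all randomized patients, and the window for counting responses closes at progression or subsequent anti-cancer therapy, not when treatment stops. The point concerns safety conduct, and the sample size and primary test are unaffected.

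**What to change.** 1. Change the skin row to: Grade 3, withhold; Grade 4, permanently discontinue.
2. Add one note to Table 2: for a drug-related Grade 4 event, the general Grade 4 row takes precedence over the withhold rows, except for its listed exceptions. State in the same place that the anemia note does not override this.

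Adding anemia to the exception list would not be enough by itself if the sponsor wants to allow withholding, because the row for life-threatening related events would still require stopping.

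The cost is a short protocol amendment. Table 3 and the SAP, whose Section 6.6.1.2.1 repeats the Table 3 schedule, stay as they are.

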6.4.1.2 Pembrolizumab

Pembrolizumab dosing can be withheld up to 12 weeks according to [Table 4](#), based on the most current package insert, dated July 2018. This document can be downloaded from the following Web sites:

FDA home page:

<https://www.accessdata.fda.gov/scripts/cder/daf/index.cfm?event=overview.process&ApplN=125514>,

DailyMed: <https://dailymed.nlm.nih.gov/dailymed/drugInfo.cfm?setid=9333c79b-d487-4538-a9f0-71b91a02b287#S5.1>,

Please ensure you are using the most current version of the package insert as updates by drug manufacturers are continuous.

Pembrolizumab infusion-related reactions should be managed according to [Table 5](#).

Patients may resume treatment with pembrolizumab when drug-related AE(s) resolve(s) to Grade ≤ 1 or baseline value, with the following exceptions:

- Patients may resume treatment in the presence of Grade 2 fatigue.
- Patients who have not experienced a Grade 3 drug-related skin adverse event may resume treatment in the presence of Grade 2 skin toxicity.
- Patients with baseline AST/ALT or total bilirubin in the Grade 1 toxicity range who require dose withhold for reasons other than a 2-grade shift in AST/ALT or total bilirubin may resume treatment in the presence of Grade 2 AST/ALT or total bilirubin.
- Drug-related endocrinopathies adequately controlled with only physiologic hormone replacement may resume treatment.

Patients who do not meet the minimum re-treatment criteria on Day 21 of the cycle and do not meet the criteria for discontinuation will withhold treatment and be followed for resolution of toxicity to levels specified in package insert for resuming pembrolizumab.

Dose reduction is not permitted for pembrolizumab.

Table 4. Dose Modification and Toxicity Management Guidelines for Immune-Related AEs Associated with Pembrolizumab


General instructions:
 
Corticosteroid taper should be initiated upon AE improving to Grade 1 or less and continue to taper over at least 4 weeks.
 
For situations in which pembrolizumab has been withheld, pembrolizumab can be resumed after AE has been reduced to Grade 1 or 0 and corticosteroid has been tapered. Pembrolizumab should be permanently discontinued if AE does not resolve within 12 weeks of last dose or corticosteroids cannot be reduced to ≤ 10 mg prednisone or equivalent per day within 12 weeks.
 
For severe and life-threatening immune-related AEs, IV corticosteroid should be initiated first followed by oral steroid. Other immunosuppressive treatment should be initiated if immune-related AEs cannot be controlled by corticosteroids.
				
Immune-related AEs	Toxicity grade or conditions (CTCAEv4.03)	Action taken to pembrolizumab	irAE management with corticosteroid and/or other therapies	Monitor and follow-up
Pneumonitis	Grade 2	Withhold	Administer corticosteroids (initial dose of 1-2 mg/kg prednisone or equivalent) followed by taper	
Monitor participants for signs and symptoms of pneumonitis.
 
Evaluate participants with suspected pneumonitis with radiographic imaging and initiate corticosteroid treatment.
 
Add prophylactic antibiotics for opportunistic infections.

	Grade 3 or 4 or recurrent Grade 2	Permanently discontinue		
Diarrhea/Colitis	Grade 2 or 3	Withhold	Administer corticosteroids (initial dose of 1-2 mg/kg prednisone or equivalent) followed by taper	
Monitor participants for signs and symptoms of enterocolitis (ie, diarrhea, abdominal pain, blood or mucus in stool with or without fever) and of bowel perforation (ie, peritoneal signs and ileus).
 
Participants with \geqGrade 2 diarrhea suspecting colitis should consider GI consultation and performing endoscopy to rule out colitis.
 
Participants with diarrhea/colitis should be advised to drink liberal quantities of clear fluids. If sufficient oral fluid intake is not feasible, fluid and electrolytes should be substituted via IV infusion.

	Grade 4	Permanently discontinue		
AST/ALT elevation or Increased bilirubin	Grade 2	Withhold	Administer corticosteroids (initial dose of 0.5-1 mg/kg prednisone or equivalent) followed by taper	
Monitor with liver function tests (consider weekly or more frequently until liver enzyme value returned to baseline or is stable).

	Grade 3 or 4	Permanently discontinue	Administer corticosteroids (initial dose of 1-2 mg/kg prednisone or equivalent) followed by taper	

Type 1 diabetes mellitus (T1DM) or Hyperglycemia	Newly onset T1DM or Grade 3 or 4 hyperglycemia associated with evidence of β -cell failure	Withhold	Initiate insulin-replacement therapy for participants with T1DM Administer anti-hyperglycemic in participants with hyperglycemia	Monitor participants for hyperglycemia or other signs and symptoms of diabetes.
Hypophysitis	Grade 2	Withhold	Administer corticosteroids and initiate hormonal replacements as clinically indicated	Monitor for signs and symptoms of hypophysitis (including hypopituitarism and adrenal insufficiency).
	Grade 3 or 4	Withhold or permanently discontinue		
Hyperthyroidism	Grade 2	Continue	Treat with non-selective beta-blockers (eg, propranolol) or thionamides as appropriate	Monitor for signs and symptoms of thyroid disorders.
	Grade 3 or 4	Withhold or permanently discontinue		
Hypothyroidism	Grades 2-4	Continue	Initiate thyroid-replacement hormones (eg, levothyroxine or liothyronine) per standard of care	Monitor for signs and symptoms of thyroid disorders.
Nephritis and renal dysfunction	Grade 2	Withhold	Administer corticosteroids (prednisone 1-2 mg/kg or equivalent) followed by taper	Monitor changes of renal function.
	Grade 3 or 4	Permanently discontinue		
Myocarditis	Grade 1 or 2	Withhold	Based on severity of AE administer corticosteroids	Ensure adequate evaluation to confirm etiology and/or exclude other causes.
	Grade 3 or 4	Permanently discontinue		
All other immune-related AEs	Intolerable/persistent Grade 2	Withhold	Based on type and severity of AE administer corticosteroids	Ensure adequate evaluation to confirm etiology and/or exclude other causes
	Grade 3	Withhold or discontinue based on the type of event. Events that require		

		discontinuation include, and are not limited to: Guillain-Barre Syndrome, encephalitis		
	Grade 4 or recurrent Grade 3	Permanently discontinue		

Withholding or permanently discontinuing pembrolizumab is at the discretion of the investigator or treating physician.

NOTE:

For participants with Grade 3 or 4 immune-related endocrinopathy for whom withhold of pembrolizumab is required, pembrolizumab may be resumed when AE resolves to \leq Grade 2 and is controlled with hormonal-replacement therapy or achieved metabolic control (in case of T1DM).

Abbreviations: AE = adverse event; ALT = alanine transaminase; AST = aspartate aminotransferase; CTCAE = Common Terminology Criteria for Adverse Events; GI = gastrointestinal; irAE = immune-related adverse event; IV = intravenous; T1DM = Type 1 diabetes mellitus.

Note: Patients who have asymptomatic or clinically non-significant Grade 3 or 4 lipase or amylase elevations (that is, not associated with clinical symptoms or radiological signs of pancreatitis) that are transient as demonstrated by a decrease of at least 1 CTCAE Grade within 7 days ± 3 days of onset will not require pembrolizumab discontinuation or modification. If the elevation has not decreased at least 1 CTCAE Grade within this time window, pembrolizumab treatment may only continue after consultation and discussion with the Sponsor.

Table 5. Pembrolizumab Infusion-Related Reaction Treatment Guidelines

NCI CTCAE Grade	Treatment	Premedication at Subsequent Dosing
Grade 1	Increase monitoring of vital signs as medically indicated until the patient is deemed medically stable in the opinion of the investigator.	None
Grade 2	
Stop infusion and monitor symptoms.
 
Additional appropriate medical therapy may include, but is not limited to:
 
 • IV fluids • Antihistamines • NSAIDS • Acetaminophen • Narcotics 
Increase monitoring of vital signs as medically indicated until the patient is deemed medically stable in the opinion of the investigator.
 
If symptoms resolve within 1 hr of stopping drug infusion, the infusion may be restarted at 50% of the original infusion rate (eg, from 100 mL/hr to 50 mL/hr). Otherwise, dosing will be held until symptoms resolve and the patient should be premedicated for the next scheduled dose.
 
Patients who develop Grade 2 toxicity despite adequate premedication should be permanently discontinued from further trial treatment administration.
	
Patient may be premedicated 1.5 hr (\pm30 minutes) prior to infusion of pembrolizumab (MK-3475) with: Diphenhydramine 50 mg po (or equivalent dose of antihistamine). Acetaminophen 500-1000 mg po (or equivalent dose of antipyretic).

Pembrolizumab Infusion-Related Reaction Treatment Guidelines

NCI CTCAE Grade	Treatment	Premedication at Subsequent Dosing
Grades 3 or 4 Grade 3: Prolonged (ie, not rapidly responsive to symptomatic medication and/or brief interruption of infusion); recurrence of symptoms following initial improvement; hospitalization indicated for other clinical sequelae (eg, renal impairment, pulmonary infiltrates) Grade 4: Life-threatening; pressor or ventilatory support indicated	Stop Infusion Additional appropriate medical therapy may include, but is not limited to: 
 • IV fluids • Antihistamines • NSAIDS • Acetaminophen • Narcotics • Oxygen • Pressors • Corticosteroids • Epinephrine Increase monitoring of vital signs as medically indicated until the patient is deemed medically stable in the opinion of the investigator. Hospitalization may be indicated. Patient is permanently discontinued from further trial treatment administration.	No subsequent dosing.

Appropriate resuscitation equipment should be available in the room and a physician readily available during the period of drug administration.

Abbreviations: IV = intravenous; NCI CTCAE = National Cancer Institute Common Terminology Criteria for Adverse Events; NSAID = non-steroidal anti-inflammatory drug; po = by mouth.

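### Table 4 withholds pembrolizumab for Grade 1 myocarditis, but the general resume rules permit re-dosing at Grade 1 and no exception covers myocarditis

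*Protocol*

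**What the plan says.** All of the following is in Protocol 6.4.1.2 unless another section is named.

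- **Myocarditis row of Table 4.** Grade 1 or 2: withhold. Grade 3 or 4: permanently discontinue. The steroid column reads "Based on severity of AE administer corticosteroids", and the monitoring column reads "Ensure adequate evaluation to confirm etiology and/or exclude other causes".
- **General instructions of Table 4.** After a withhold, "pembrolizumab can be resumed after AE has been reduced to Grade 1 or 0 and corticosteroid has been tapered". On steroids: "Corticosteroid taper should be initiated upon AE improving to Grade 1 or less and continue to taper over at least 4 weeks". On the time limit: "Pembrolizumab should be permanently discontinued if AE does not resolve within 12 weeks of last dose".
- **Section text before the table.** "Patients may resume treatment with pembrolizumab when drug-related AE(s) resolve(s) to Grade" 1 or lower, or to baseline. Four exceptions follow, for fatigue, skin toxicity, liver tests and endocrinopathy. The last reads "Drug-related endocrinopathies adequately controlled with only physiologic hormone replacement may resume treatment".
- **Package insert.** Patients who fail the minimum re-treatment criteria on Day 21, and who need not discontinue, are followed until toxicity falls to "levels specified in package insert for resuming pembrolizumab".
- **Notes under Table 4.** One gives a resume rule for Grade 3 or 4 endocrinopathy. Another deals with lipase and amylase. A separate sentence leaves the decision to withhold or stop pembrolizumab to the investigator or treating physician.
- **Section 6.4.** Continued treatment rests on the investigator's weighing of risk and benefit under these guidelines. In Arm 1, stopping one study drug stops both.

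**The concern.** A withhold rule and a resume rule normally leave a gap, so that a patient has to improve out of the withhold range before the next dose. For myocarditis the withhold range reaches down to Grade 1, while the general resume rules reach up to Grade 1. A patient whose myocarditis has improved but not cleared can therefore be re-dosed within the stated rules. Two sites could also treat the same Grade 1 patient in opposite ways, one following the row and the other the general instruction, and both would be compliant. What is at stake is patient safety and consistent conduct. The efficacy analysis is not at issue.

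**Working it through.** The plan gives no figure to reproduce here. The check compares grade sets in the text.

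**Step 1. Myocarditis.** Withhold grades from the row: {1, 2}. Resume grades from the general instruction: {0, 1}; the section text gives the same set, or baseline. The overlap is {1}.

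**Step 2. Is this specific to myocarditis?** Table 4 has ten event rows, and nine of them include a withhold action (hypothyroidism is always continue). Gap = lowest graded withhold trigger minus the highest general resume grade, which is 1.

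| Rows | Lowest graded withhold trigger | Gap |
|---|---|---|
| Pneumonitis, diarrhea/colitis, liver tests, hypophysitis, nephritis, other immune-related events (6 rows) | 2 | 2 − 1 = 1 |
| Hyperthyroidism; hyperglycemia part of the diabetes row (2 rows) | 3 | 3 − 1 = 2 |
| Myocarditis (1 row) | 1 | 1 − 1 = 0 |

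The rows add up: 6 + 2 + 1 = 9. The new-onset type 1 diabetes part of the diabetes row carries no grade and has no gap to compute. Among graded triggers, only myocarditis includes Grade 1.

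**Step 3. Does any exception close the overlap?** The four exceptions in the section text and the endocrinopathy note permit dosing to resume above Grade 1 or on hormone replacement. They loosen the general rule for named events; the one for Grade 2 fatigue carries no further condition. The lipase and amylase note concerns those enzymes only. None mentions myocarditis, and none sets a resume level stricter than Grade 1.

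**Step 4. Which patients are affected?**

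- *Grade 2 improving to Grade 1.* The event has been reduced to Grade 1, so both general rules are met once any steroid is tapered. The row still lists Grade 1 as a withhold grade.
- *Grade 1 from the start, and unchanged.* The table speaks of an event that has been reduced, and the section text of one that resolves to Grade 1 or lower. Whether an unchanged Grade 1 event satisfies either is unclear.

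**Step 5. Do the timing rules settle it?** If steroid is given, the taper of at least 4 weeks delays re-dosing. The row makes steroid depend on severity, so a mild event may receive none, and the section text attaches no taper condition. The 12-week limit names no grade for re-dosing before it is reached. It does not define resolution, and the section text speaks of resolving to Grade 1 or lower. The evaluation of cause is required but is not made a condition of re-dosing.

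**The case against.** The strongest reply is that a trigger and a recovery threshold do different jobs. The row says what to do when the event appears; the general instruction says when a withheld drug may return. Read in that order, Grade 2 falling to Grade 1 is covered. The resume wording is permissive throughout, the sentence under Table 4 and Section 6.4 leave the decision to the physician, and the package insert, to which the section defers, may be stricter.

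Much of this stands and limits the severity. No patient has to be re-dosed at Grade 1. The insert is not among the documents, so the protocol cannot be said to depart from it. But none of these points supplies a resume level for myocarditis. The sentence that sends patients to the insert applies to those who do not meet the re-treatment criteria, and a Grade 1 patient already meets the criterion in the section text. Reading the rules in sequence also leaves the Grade 1 part of the row with little effect.

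A reader might infer three stronger points that the documents do not support:

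- *That a definite number of doses would be given at Grade 1 before week 12.* The limit runs from the last dose, so on a plain reading each new dose moves it. A count against a fixed day is not sound.
- *That a given number of patients would be affected.* The documents state no incidence of myocarditis.
- *That Grade 0 follows logically from the Grade 1 trigger.* Equal trigger and recovery thresholds are possible, and which level is clinically right cannot be settled from the text.

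**Conclusion.** The concern holds as a conflict between stated rules: myocarditis is withheld at Grade 1 and may be resumed at Grade 1, with nothing to reconcile the two. Its size is one grade in one of the nine Table 4 rows with a withhold action. The wording overlap is certain for a Grade 2 event that improves to Grade 1 and is an ambiguity for one that stays at Grade 1.

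I rate it minor, and worth correcting because the correction is cheap. The rating assumes that myocarditis is rare in about 100 patients and that physicians use the discretion they are given. It also takes into account the steroid taper where steroid is given and the 12-week stop. No effect on ORR, power or type I error is claimed.

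**What to change.** Add to the myocarditis row of Table 4, and repeat as an exception in the text of 6.4.1.2, that pembrolizumab may resume only when all three conditions are met:

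- the event has resolved to Grade 0 or baseline;
- the evaluation of cause is complete;
- any corticosteroid has been tapered.

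If they are not met by 12 weeks, discontinue permanently. Grade 0 is the smallest change that removes the overlap. The sponsor should confirm it clinically and against the current package insert before adopting it. The endocrinopathy note shows that Table 4 already accommodates an event-specific resume rule.

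The cost is one table line and one exception, with no extra scheduled visits. The downside is some missed pembrolizumab doses, or a permanent stop, in a rare patient. In Arm 1 a permanent stop would also end AM0010 under Section 6.4.
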